8.4.3 Pregnancy and assessments of fertility

Medical documentation of oophorectomy, hysterectomy, or tubal ligation must be retained as source documents. Subsequent hormone level assessment to confirm the woman is not of child-bearing potential must also be available as source documentation in the following cases:

- 1. Surgical bilateral oophorectomy without a hysterectomy
- 2. Reported 12 months of natural (spontaneous) amenorrhea with an appropriate clinical profile.

In the absence of the above medical documentation, FSH testing is required of any female participant regardless of reported reproductive/menopausal status at screening/baseline.

All pre-menopausal women who are not surgically sterile will have pregnancy testing. Additional pregnancy testing might be performed if requested by local requirements.

At screening, a serum pregnancy test (serum β -HCG) must be performed within 3 days (72 hours) before the first dose.

During the study, a urine/serum pregnancy test should be performed at Day 1 of each cycle (except Cycle 1 if a pregnancy test had been performed within 72 hours of the first dose) and a serum pregnancy test at EOT visit. Pregnancy testing (urine/serum) should occur at monthly intervals during the 150-day safety follow-up period. Refer to Table 8-1 for pregnancy testing schedule.

A positive urine pregnancy needs to be confirmed with a serum test. Confirmed positive pregnancy test requires immediate discontinuation of study treatment and discontinuation from study. See Section 10.1.4 for pregnancy reporting.

The pregnancy tests will be recorded only in the source documentation, not in the CRF.

Women of childbearing potential should employ the use of highly effective contraception during study treatment, for 90 days after the last dose of azacitidine, 30 days after the last dose of venetoclax (or as per their respective local labels, whichever is longer) and 150 days after the last dose of sabatolimab. Highly effective contraception methods are defined in Section 5.2.

A condom is required for all sexually active male participants to prevent them from fathering a child AND to prevent delivery of study treatment via seminal fluid to their partner while taking azacitidine and for 3 months after stopping this drug. In addition, male participants should not donate sperm for the time period specified above.

8.4.4 Appropriateness of safety measurements

Overall, the safety assessments selected are standard for this indication/participant population.

Additionally, given the unique clinical setting and limited information about the use of sabatolimab in combination with azacitidine and venetoclax, the study employs a two part design with a halt to enrollment following the Safety run-in part of the study as explained in Section 4.1.

8.5 Additional assessments

8.5.1 Clinical Outcome Assessments (COAs)

The Functional Assessment of Chronic Illness Therapy Fatigue scale (FACIT-Fatigue) is a 13item PRO measure designed to assess fatigue in people with cancer (Yellen et al 1997). It includes seven items that assess fatigue-related symptoms and six items that assess impacts of fatigue on daily activities and function over the past seven days. The higher the score, the better the quality of life. The score ranges from 0 to 52, and a score of less than 30 indicates severe fatigue.

All global items will be used to assign clinical meaning to observed group differences e.g., to generate clinically important difference (CID estimates) and within person change (e.g., to generate clinically important response estimates) in the on the FACIT Fatigue total score from the participant perspective.

Participants will be prompted to complete all PRO questionnaires via a provisioned ePRO device at time-points indicated in Table 8-1. At baseline, the questionnaire(s) will be completed prior to any interaction with the study investigator including any tests, treatments or receipt of results from any tests to avoid biasing participant responses to study questionnaires. The participant will be provided an ePRO device to be able to complete the PROs at home the day prior to visits to the clinic site as indicated. Please refer to the study ePRO manual for detailed instructions for completion and handling of the ePROs.

The PRO measure(s) should be completed in the order they appear on ePRO device.

8.5.2 Pharmacokinetics

Pharmacokinetic (PK), Immunogenicity (IG) samples samples will be obtained and evaluated in all participants. Please refer to Table 8-9 and Table 8-10 for details on PK, IG sample collections. If participants experience an SAE or an AE leading to the discontinuation of the study treatment, an unscheduled PK blood sample should be obtained as close as possible to the event occurrence. The date and time of the last dose and the time of PK blood draw should be recorded. If participants experience suspected immunologically related AE such as infusion-related reaction, hypersensitivity, cytokine release syndrome and anaphylaxis, an unscheduled IG blood sample should be obtained as close as possible to the event occurrence. The date and time of PK blood draw should be recorded.

8.5.2.1 Pharmacokinetic blood collection and handling

The sabatolimab PK, and IG blood sampling schedule is outlined in Table 8-9. A single blood sample of approximately 5 mL will be collected at each time point.

Confidential

Blood samples will be taken by either direct venipuncture or an indwelling cannula inserted in a forearm vein opposite to the arm used for infusion. When PK is collected at the same time point as ECG, the PK sample should be taken immediately after ECG.

The exact date and clock times of drug administration and blood draws for PK, IG assessment will be recorded on the appropriate eCRF.

After permanent discontinuation of sabatolimab, the samples scheduled for pre-sabatolimab infusion should no longer be collected.

Detailed instructions for the collection procedures, handling, and shipment of sabatolimab PK, IG and venetoclax PK samples will be provided in the [CMBG453B12203]

Table 8-9	Sabatolima	ıb PK, IG	blood col	lection log	
Cycle	Day	Scheduled Time Point*	PK sample (sabatolima b)	IG sample	
1	1	Pre- azacitidine/ venetoclax dose			
	8	Pre- sabatolimab infusion	X	X	
2	8	Pre- sabatolimab infusion	Х	X	
3	8	Pre- sabatolimab infusion	X	X	
6	8	Pre- sabatolimab infusion	X	X	
9	8	Pre- sabatolimab infusion	X	X	
12	8	Pre- sabatolimab infusion	X	X	

Laboratory Manual].

Cycle	Day	Scheduled Time Point*	PK sample (sabatolima b)	IG sample	
18	8	Pre- sabatolimab infusion	Х	Х	
24	8	Pre- sabatolimab infusion	Х	Х	
EOT ¹		Anytime	Х	Х	
30-Day Safety	/ Follow-up	Anytime	Х	Х	
150-Day Safe	ty Follow-up ²	Anytime	Х	Х	
Unscheduled ³		Anytime	Х	Х	

*All pre-dose samples should be collected within 2 hours before start of infusion ¹ If EOT is due to reasons other than disease progression, an unscheduled PK and IG sample should also be collected at the time of confirmed disease progression. 2 Samples at the 150 day safety follow-up visit can be collected at the Investigator's discretion if the follow-up visits conducted are at the site. ³Unscheduled PK and IG samples may be collected at any time if clinically indicated or at the Investigator's discretion.

Table 8-10Venetoclax PK blood collection log

Cycle	Day	Scheduled timepoint*	PK sample (venetoclax)**
1	8	Pre-venetoclax dose	Х
3	8	Pre-venetoclax dose	Х

*All pre-dose samples must be collected within 30 min before dose administration ** Venetoclax PK samples will be collected only during Part 1 (Safety run-in) of the study

8.5.2.2 Analytical method

Bioanalysis for pharmacokinetic studies will employ several validated assays:

 \cdot The assay to quantify sabatolimab will be a validated liquid chromatography mass spectrometry (LC-MS) assay.

· Plasma concentrations of venetoclax will be determined using a validated LC-MS assay.

 \cdot Immunogenicity testing will consist a multi-tiered ADA testing. A screening assay will be used to assess clinical samples. Samples testing positive in the screening assay will then be subjected to a confirmatory assay to demonstrate that ADAs are specific for the therapeutic

protein product. Samples identified as positive in the confirmatory assay will be further characterized in titration and neutralization assays.

8.5.3.1 Use of residual biological samples

If participant agrees the biological samples from the bone marrow aspirate and blood collected may be used for additional studies related to sabatolimab or hematological disease/cancer, including research to help develop ways to detect, monitor or treat cancer. Those biological samples may be stored for up to 15 years after the end of the study and the decision to perform such research studies would be based on outcome data from this study or from new scientific findings related to the drug class or disease, as well as assay availability.

Confidential

9 Study discontinuation and completion

9.1 Discontinuation and completion

9.1.1 Study treatment discontinuation and study discontinuation

Discontinuation of study treatment will occur when a participant meets any of the reasons described below, and can be initiated by either the participant or the investigator.

The investigator must discontinue study treatment for a given participant if, he/she believes that continuation would negatively impact the participant's well-being.

Study treatment must be discontinued under the following circumstances:

· Participant/guardian decision

· Pregnancy

 \cdot Use of prohibited treatment as per recommendations in the prohibited treatment section (Section 6.2.2)

· Any situation in which study participation might result in a safety risk to the participant

 \cdot Any adverse events or laboratory abnormalities that in the judgment of the investigator, taking into consideration the participant's overall status, prevents the participant from continuing participation in the study

· Progression of disease (including transformation to acute leukemia per WHO 2016 classification, as defined as \geq 20% blasts in bone marrow and/or peripheral blood),

· Termination of the study by Novartis

 \cdot Subjects who are scheduled for hematopoietic stem cell transplant (HSCT) or intensive chemotherapy at any time during the course of the study

If discontinuation of study treatment occurs, the investigator should make a reasonable effort to understand the primary reason for the participant's premature discontinuation of study treatment and record this information.

Participants who discontinue study treatment or who decide they do not wish to participate in the study further should NOT be considered withdrawn from the study UNLESS they withdraw their consent (see 'Withdrawal of Informed Consent' Section 9.1.2). Where possible, they should return for the assessments indicated in the Assessment Schedule. If they fail to return for these assessments for unknown reasons, every effort (e.g. telephone, e-mail, letter)

should be made to contact the participant/pre-designated contact as specified in the lost to follow-up section. This contact should preferably be done according to the study visit schedule.

If the participant cannot or is unwilling to attend any visit(s), the site staff should maintain regular telephone contact with the participant, or with a person pre-designated by the participant. This telephone contact should preferably be done according to the study visit schedule.

The investigator must also contact the IRT to register the participant's discontinuation from study treatment.

If discontinuation of study treatment occurs due to protocol defined reasons, participants will be followed for efficacy, safety and survival as detailed in Section 9.1.1.1, Section 9.1.1.2 and Section 9.1.1.3.

9.1.1.1 Safety follow-up

All participants must be followed for safety for 150 days after the last dose of sabatolimab or 30 days after the last dose of azacitidine or venetoclax whichever is longer.

After the 30-Day on-site safety follow-up visit, participants will be followed via telephone call (or on-site visit if participant happens to be visiting the site) at 90 and 150 days after the last dose of sabatolimab. All safety assessments should be completed as per Table 8-1. However, if the participant begins new antineoplastic medication before the end of the safety follow-up period, the collection of new SAEs and AEs unrelated to study medication will stop and thereafter only suspected AEs and suspected SAEs will continue to be collected up to the end of the safety follow-up period. For female participants of childbearing potential, a pregnancy test will be performed at the timepoints listed in Table 8-1.

9.1.1.2 Post-treatment follow-up

For participants who discontinue treatment for reasons other than disease progression, death, lost to follow-up, or withdrawal of consent; efficacy assessments, and other required assessments will continue to be performed as per the assessment schedule (see Table 8-1) until disease progression, death, lost to follow-up, or withdrawal of consent.

9.1.1.3 Survival follow-up

Participants will enter the survival follow-up period in parallel with the safety follow-up or efficacy follow-up periods. Participants will then be contacted by telephone every 12 weeks to follow-up on their survival status. Any new antineoplastic therapies that have been started since the previous contact will be collected. HSCT information will also be collected during these phone calls.

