•	To assess duration of CR	•	Duration of CR is defined as time from first occurrence of CR to relapse from CR, progression or death due to any cause whichever occurs first for participants treated with sabatolimab at 800 mg Q4W.		
•	To assess time to CR/mCR	•	Time to CR/mCR is defined as time from start of treatment to first occurrence of CR or mCR as per investigator assessment for participants treated with sabatolimab at 800 mg Q4W.		
•	To assess duration of CR/mCR	•	Duration of CR/mCR is defined as time from first occurrence of CR/mCR to relapse from CR, progression or death due to any cause whichever occurs first for participants treated with sabatolimab at 800 mg Q4W.		
•	To assess duration of response (responding participants defined as hematological improvement (HI) or better, per modified IWG-MDS	•	Duration of response for participants who achieved HI or better per modified IWG-MDS Cheson 2006 criteria) as per investigator assessment until relapse or death. Participants who did not relapse or die are censored to last adequate response assessment		

Objective(s)	Endpoint(s)		
Cheson 2006 criteria) as per investigator assessment.	for participants treated with sabatolimab at 800 mg Q4W.		
 To assess Progression-Free Survival (PFS) 	• Time from start of treatment to disease progression (including transformation to acute leukemia per WHO 2016 classification), relapse from CR or death due to any cause, whichever occurs first for participants treated with sabatolimab at 800 mg Q4W.		
 To assess Leukemia-Free Survival (LFS) 	 Time from start of treatment to transformation to acute leukemia [as defined as ≥ 20% blasts in bone marrow/ peripheral blood (per WHO 2016 classification) or diagnosis of extramedullary acute leukemia or death due to any cause, whichever occurs first] for participants treated with sabatolimab at 800 mg Q4W. 		
 To assess Event-free Survival (EFS) 	• Time from start of treatment to lack of reaching CR within the first 6 cycles, relapse from CR or death due to any cause, whichever occurs first for participants treated with sabatolimab at 800 mg Q4W.		
To assess Overall Survival (OS)	• Time from start of treatment to death due to any cause for participants treated with sabatolimab at 800 mg Q4W.		
• Expansion (Part 2)			
• To avaluate the changes from			

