6.1.5.1 Treatment beyond disease progression

Treatment beyond disease progression is not permitted.

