	2. Decrease of $\geq 50\%$ from maximum remission/response*** levels in neutrophils AND neutrophils $<1.0*10^{9}/L$. Note: neutrophils counts during periods of active infection will not be considered in determining the maximum
	3. Decrease of \geq 50% from maximum remission/response*** levels in platelets AND platelets < $100*10^{9}/L$
	4. Decrease from maximum remission/response*** levels in Hgb concentration by ≥ 1.5 g/dL AND Hgb < 10 g/dL
	5. Becoming transfusion dependent**
Disease progression	At least 1 of the following criteria is met:

Response category	Definition [#]
	[in absence of another explanation not due to MDS, such as acute infection, bleeding, hemolysis, etc. Note that observation of peripheral blasts is not a sufficient criterion for progression. However in that case, a bone marrow examination should be made to determine whether relapse has occurred]
	Bone marrow according to the number of blasts of the participant at baseline:
	1. Less than 5% blasts at baseline : \geq 50% increase in blasts over baseline to > 5% blasts
	2. 5% - < 10% blasts at baseline : \geq 50% increase over baseline to > 10% blasts
	3. $10\% - < 20\%$ blasts at baseline : $\ge 50\%$ increase over baseline to $> 20\%$ blasts.
	Participants with more than 20% of blasts will be considered to have transformation to acute leukemia per 2016 WHO classification (Arber et al, 2016)
	Peripheral blood:
	1. Decrease of $\geq 50\%$ from maximum remission/response*** levels in neutrophils AND neutrophils < $1.0*10^9/L$. Note: neutrophils counts during periods of active infection will not be considered in determining the maximum
	2. Decrease of \geq 50% from maximum remission/response*** levels in platelets AND platelets < $100*10^9/L$
	3.Reductionfrommaximumremission/response***levelsinHgbby2g/dLANDHgb $10g/dL$
	Becoming transfusion dependent**
	Occurrence of acute leukemia, or extramedullary leukemia per investigator's judgement

Modified Hematologic Improvement per IWG-MDS criteria (Cheson et al 2006)

Response category	Definition [#]
HI category	Definition [#] (HI must last at least 8 weeks)
Erythroid response (HI-E) (pretreatment*, <11 g/dL)	1. Hgb increase from baseline by \geq 1.5 g/dL, in at least 2 consecutive Hgb measurements and maintained over at least 8 weeks

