The efficacy follow-up period will last until participant's documented disease progression (per IWG criteria Table 8-2), death, lost to follow-up, or withdrawal of consent, or the end of the study whichever comes first. Post-treatment antineoplastic therapies, including HSCT, will continue to be captured during survival follow-up (see Section 9.1.1.3 and Table 8-1).

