Progression free survival (PFS)

PFS is defined as the time from start date of treatment to date of relapse, progression (including transformation to acute leukemia per WHO 2016 classification) or death due to any cause. If a participant is not known to have relapsed progressed nor died, PFS will be censored at the last adequate response assessment (on or before the cut-off date). Progression/relapse or death after HSCT, interruptions, or discontinuation of study treatment due to any reason will be taken into account. However, Progression/Relapse, death occurring after initiation of new antineoplastic therapy will not be considered as event and PFS will be censored at last adequate response assessment.

In case of two or more missing assessments prior to documented progression, relapse or death, PFS will be censored at the last adequate response assessment prior to the documentation of progression, relapse or death.

PFS will be estimated using the Kaplan-Meier method. The median PFS along with 95% confidence interval will be presented.

Leukemia free survival (LFS)

LFS is defined as the time from start of treatment to transformation to acute leukemia as per investigator assessment defined as the following:

- $\geq 20\%$ blasts in bone marrow/ peripheral blood (per WHO 2016 classification)
- Diagnosis of extramedullary acute leukemia
- Death due to any cause

whichever occurs first.

If a participant is known to not have progressed to leukemia, then LFS will be censored at the last bone marrow/peripheral blood assessments (on or before the cut-off date). All of three events ($\geq 20\%$ blasts in bone marrow/peripheral blood, diagnosis of extramedullary acute leukemia or death) after HSCT, interruptions, or discontinuation of study treatment due to any reason will be taken into account. However, events occurring after initiation of new antineoplastic therapy will not be considered as event and LFS will be censored at last assessment of bone marrow/peripheral blood, diagnosis of extramedullary acute leukemia or survival follow-up prior to initiation of new antineoplastic therapy.

LFS will be estimated using the Kaplan-Meier method. The median LFS along with 95% confidence interval will be presented.

Overall Survival (OS)

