If a participant is known to not have progressed to leukemia as defined by the criteria mentioned above, then LFS will be censored at the last bone marrow/peripheral blood assessments (on or before the cut-off date). Any of the three events (i.e. $\geq 20\%$ blasts in bone marrow/peripheral blood, diagnosis of extramedullary acute leukemia or death) occurring after HSCT, interruptions, or discontinuation of study treatment due to any reason will be taken into account. However, events occurring after initiation of new antineoplastic therapy will not be considered

an event and LFS will be censored at the last adequate assessment of bone marrow and/or peripheral blood, or diagnosis of extramedullary acute leukemia prior to initiation of new antineoplastic therapy.

In case of two or more missing assessments prior to documented progression to leukemia, LFS will be censored at the last adequate assessment (bone marrow and/or hematology assessment) prior to the documentation of progression to leukemia.

LFS will be estimated using the Kaplan-Meier method. The median LFS along with 95% confidence interval will be presented.

Overall Survival (OS)

OS is defined as the time from start date of treatment to date of death due to any cause. If a participant is not known to have died, then OS will be censored at the latest date the participant was known to be alive (on or before the cut-off date). All deaths will be taken into account whenever the death occurred, i.e. even after new anti-neoplastic therapy, HSCT, interruptions, or discontinuation of study treatment due to any reason.

The OS censoring reason will be summarized as 'Alive' or 'Lost to follow-up'. Participants not known to have died will have the censoring reason 'Lost to follow-up' if the reason for discontinuation from study is 'Lost to follow-up' or 'Withdrawal of consent'. Otherwise, participants will have the censoring reason 'Alive'.

OS will be estimated using the Kaplan-Meier method. The median OS along with 95% confidence interval will be presented.

Improvement of RBC/platelets transfusion independence

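### Leukemia-free survival runs past a non-leukemic progression, but no planned assessment or follow-up question collects leukemic transformation after that point

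*Protocol*

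**What the plan says.** **Endpoint.** Protocol 12.5.1.2: "LFS is defined as the time from start of treatment to transformation to acute leukemia as per investigator assessment". The qualifying events are blasts of at least 20% in marrow or blood, extramedullary acute leukemia, or death from any cause. Table 2-1 and SAP 2.6.1.2 agree.

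**Progression without leukemia.** Table 8-2 allows progression on a blast rise that stays below 20%, on falls in neutrophils, platelets or hemoglobin, or on "Becoming transfusion dependent". None of these is an LFS event.

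**What stops at progression.** Protocol 6.1.5.1: "Treatment beyond disease progression is not permitted". Under 8.3.1 and 9.1.1.2, a participant who stops treatment because of progression does not enter efficacy follow-up. For everyone else, that phase lasts until "documented disease progression (per IWG criteria Table 8-2), death, lost to follow-up, or withdrawal of consent, or the end of the study whichever comes first". In Table 8-1, marrows after the end-of-treatment visit belong to efficacy follow-up.

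**What continues.** Protocol 9.1.1.3: "Participants will then be contacted by telephone every 12 weeks to follow-up on their survival status". The calls also collect new antineoplastic therapy and HSCT. Safety follow-up (9.1.1.1) adds contacts at 30, 90 and 150 days.

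**Censoring.** Without a leukemia event, LFS is censored at the last marrow or blood assessment. Events after new antineoplastic therapy do not count. In that case protocol 12.5.1.2 lets survival follow-up before the therapy serve as the censoring date; SAP 2.6.1.2 omits it. The SAP also censors leukemia that is documented after two or more missing assessments.

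**The concern.** LFS differs from PFS mainly in what happens after a progression that is not leukemia, and that is where planned observation of leukemia ends. Protocol 1.1 describes the transformation risk in high and very high risk MDS as high. Participants whose disease has just worsened are plausibly the ones most likely to transform next, so losing sight of them makes the censoring informative. What is then estimated is closer to leukemia up to first progression, plus deaths, than to the LFS that the objective names.

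**Working it through.** **1. Courses after a non-leukemic progression**

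| Course | LFS by its definition | LFS as the plan would record it |
|---|---|---|
| Transforms, then starts new therapy | Event at transformation | No planned record of the transformation; censored at an earlier assessment |
| Transforms, dies untreated | Event at transformation | Event at death, hence late |
| Transforms, alive and untreated at cut-off | Event at transformation | Censored at last marrow or blood assessment |
| Dies without transforming | Event at death | Event at death |

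The first three rows go wrong. All three credit too much leukemia-free time or remove an event.

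**2. Indirect routes**

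- AEs and SAEs are collected to 150 days after sabatolimab (10.1.1, 10.1.3). Once new antineoplastic medication starts, only events suspected to be related are collected, and 10.1.1 says disease progression is usually rated not suspected. The seriousness rule for new malignancies (10.1.2) excludes progression of the study indication.
- Reasons for death are collected, including post-treatment deaths (SAP 2.6.2.1, 2.6.2.3).
- New therapies are recorded and summarised (SAP 2.4.2), which may hint at leukemia but gives no diagnosis date.

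**3. The two-missing-assessments rule**

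SAP 2.6.1.3 sets the threshold at twice the scheduled interval plus the visit window:

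- 12-week schedule: 2 × 12 + 1 = 25 weeks
- 24-week schedule: 2 × 24 + 1 = 49 weeks
- 12-monthly efficacy follow-up: 2 × 52 + 2 = 106 weeks

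The SAP does not say which interval applies once no assessments are scheduled. On the 12-week threshold, a leukemia reported by telephone more than 25 weeks after the last adequate assessment would be censored back, even if it had been collected. Section 2.6.1.3 words the rule for any event; the LFS paragraph in 2.6.1.2 limits it to progression to leukemia. Its application to deaths is therefore unclear.

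**4. Size**

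The documents give no LFS rate, event count or power, so there is no figure to reproduce. The following are illustrations on assumed exponential hazards.

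*Share of transformations that come after progression.* Assumed yearly hazards: direct leukemia A = 0.15 to 0.25; non-leukemic progression P = 0.4 to 0.7; then leukemia a = 0.8 to 1.4, death d = 0.5, new therapy t = 1 to 3. With m = P × a/(a + d + t), the share is m/(A + m).

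- Low corner: m = 0.4 × 0.8/4.3 = 0.074; share = 0.074/0.324 = 23%
- High corner: m = 0.7 × 1.4/2.9 = 0.338; share = 0.338/0.488 = 69%

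Scenarios simulated inside these ranges, limited to 3 years, gave 27% to 69%.

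*24-month Kaplan-Meier LFS.* Death before progression was set at 0.15 per year, with therapy about one month after transformation:

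| Transformation collected | As planned | Difference (points) |
|---|---|---|
| 0.381 | 0.439 | +5.8 |
| 0.442 | 0.481 | +3.9 |
| 0.367 | 0.396 | +2.9 |
| 0.280 | 0.405 | +12.5 |

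*Dependence on treatment.* In a separate run within the same hazard ranges, with untreated participants dying at a median of 6 months after transformation:

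| Transformers treated | Difference at 24 months (points) |
|---|---|
| All | +3.0 to +12.0 |
| Half | +1.3 to +7.2 |
| None | -0.1 to +4.3 |

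*Median LFS.* A second model used monthly hazards: progression 0.04 to 0.05, direct leukemia 0.015 to 0.02, death 0.02; after progression, leukemia 0.03 to 0.10 and death 0.05; death after leukemia 0.115; 0 to 60% starting new therapy. At 36 months of follow-up the median is 12.3 to 15.7 months if transformation is collected. As planned, the shift is +0.3 to +3.2 months if later deaths count, and -0.2 to +2.1 months if the two-missing rule also censors late deaths. At 18 months the range is -0.6 to +3.1 months. The small negative values arise when late deaths are censored, or when survivors are censored back at their last marrow while other deaths still count.

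**The case against.** **Transformation is not invisible after progression.** The 150-day AE window, the safety contacts and the reason for death can each reveal it. This stands: a reader might infer that nothing at all records it, and that goes too far. But these routes are incomplete, and none is defined as an LFS assessment.

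**The bias may be small.** Death is an LFS event. Participants are not immediately eligible for intensive chemotherapy or HSCT at entry, and protocol 1.1 puts survival after HMA failure or transformation at usually no more than 6 months. If few transformers are treated, most are counted a little late rather than lost. This also stands. A reader might infer an overstatement of 3 to 13 points as a finding; the documents do not support that, because the range assumes that nearly all transformers start therapy.

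**The study has changed.** SAP section 1 reports the recruitment halt and that the expansion will not open. LFS now concerns only the 800 mg run-in cohort, planned at about 12 participants, and has no hypothesis or decision rule. SAP 2.6.1.2 makes Kaplan-Meier output conditional on the data. This limits the consequence without removing it: SAP 1.2 keeps every objective except fatigue, and individual LFS times with event or censoring type will be listed. In so small a cohort, one or two missing transformations would visibly change that listing.

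**Conclusion.** The gap holds on the text alone: after a non-leukemic progression, no planned assessment or follow-up question collects leukemic transformation, although LFS needs it. The expected bias is upward. Its size rests wholly on assumed hazards and on how many transformers start therapy: about zero when few do, about 12 to 13 points at 24 months when nearly all do, with slightly negative values under some censoring readings. The documents support neither a fixed overstatement nor the claim that transformation can never come to light. The practical effect is confined to LFS in the 800 mg run-in cohort, so this is a cheap improvement and not a threat to the trial's main conclusions.

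**What to change.** **Collect it.** Add to the 12-weekly survival call and its eCRF page: acute leukemia diagnosed since last contact (yes/no), date, and basis (blasts of at least 20% in marrow or blood, or extramedullary). For participants already in follow-up, obtain the same items by site query before database lock.

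**Align the analysis (SAP 2.6.1.2 and 2.6.1.3).**

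- Count a transformation recorded this way as an LFS event if it precedes new antineoplastic therapy.
- Treat each contact at which leukemia was asked about as an adequate LFS assessment, both for censoring and for the two-missing-assessments rule. Otherwise events reported by telephone could still be censored.
- State whether that rule applies to deaths in LFS.
- Reconcile the protocol and SAP wording on censoring at survival follow-up. As the protocol stands, a call that did not ask about leukemia could count as leukemia-free time.

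**If not done,** state in the CSR that transformation was systematically collected only up to first progression.

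**Cost.** One question on a call already made, one small eCRF block and a few SAP sentences; no extra visit or marrow. Changing the call needs a protocol amendment under 14.1, or a site query in its place. Transformations after progression would be dated from local records.
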